6.2. Eligibility

Inclusion Criteria: In order to be eligible to participate in this study, an individual must meet **all** of the following criteria:

- Non-Latino Black women
- Over 18 years of age,
- Have a BMI ≥ 25 kg/m²
- Use a Bluetooth-enabled smartphone
- Report at least one binge eating episode weekly

Exclusion Criteria: Any individual who meets one or more of the following criteria will be excluded from participation:

- Individuals who are currently pregnant,
- In substance use treatment,
- Currently receiving psychological or pharmacological treatment for disordered eating or eating disorders,
- Children (under the age of majority for their location),
- Nonviable neonates or neonates of uncertain viability,
- Prisoners, other involuntarily detained or incarcerated (this includes parolees help in treatment centers as a condition of their parole),
- Decisionally impaired individuals,
- Children who are wards of the State (Foster children),
- Non-English-speaking individuals,
- People, including children, who are likely to be involved in abusive relationships, either as perpetrator or victim

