Study Title	Reducing Binge Eating to Prevent Weight Gain in Black Women
Objectives	
Primary: Examine the feasibility and acceptability of a 6-month AAT + NUTR (N=48) intervention. AA women (BMI ≥ 25 kg/m²) with weekly binge eating episodes will be randomized to the AAT+NUTR (n=24) or wait-list control (n=24). The study will examine recruitment, retention, barriers to completion, satisfaction, and adherence.
 
Secondary: At 4 (end of treatment) and 6 months (follow-up), examine changes in (a) binge eating; (b) depressive symptoms; (c) dietary outcomes (e.g., overall energy intake, fat, fruit and vegetable intake); and (d) weight for participants in each group.
 
Tertiary/Exploratory: Conduct key informant interviews (n=15-20) with UNC Department of Family Medicine staff and participants to determine acceptability of the AAT intervention in the primary care setting.

Target Population	
Key Inclusion Criteria Individuals are eligible if they are non-Latino Black women, over 18 years of age, have a BMI ≥ 25kg/m², use a Bluetooth-enabled smartphone, report at least one binge eating episode weekly, and complete the screening.
 
Key Exclusion Criteria Individuals will be excluded if they are currently pregnant, in substance use treatment, involved in a weight loss program, have a history of anorexia nervosa, engage in purging, are currently receiving psychological or pharmacological treatment for disordered eating or eating disorders, or are concurrent intravenous drug users or consume >4 alcoholic beverages/day.

Numbers of Participants	
Number to be recruited for screening [some will not be eligible for enrollment] 200
 
Number of eligible participants enrolled [this is the target sample size for enrollment] 60

Clinical Phase	[I, II, III, or IV (if applicable)]

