5.4. Outcome Measures

Primary Outcome(s):

Table 2: Feasibility Measures (Aim #1) ³⁸	
Question of Interest	Feasibility Measures
Can we recruit our target population?	# of screened and eligible participants, and proportion of eligible screens who enroll
Will participants do what they are asked to do?	Adherence to study protocol (e.g. session attendance, homework completion)
Are the assessments too burdensome?	Proportion of planned assessments completed; duration of assessment visits
Will participants stay in the study?	% of study retention and reasons for dropouts
Is AAT + NUTR acceptable to study participants?	Semi-structured telephone interviews (n=15-20) will be conducted to receive feedback on intervention and suggestions for improvement.

Secondary Outcome(s): Linear mixed effects modeling will be used to examine the association between treatment group assignment (AAT + BWL or wait-list control group coded as a (0,1)-indicator) and binge eating, eating self-efficacy, depressive symptoms, weight, blood pressure, and waist circumference scores at 2 and 6 months.

6. Study Participants

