6.4. Consent Process

If participants are eligible for the study, the applicant will be given a date and time to meet with the PI and will be provided an email link to access the self-report measures associated with this study. At appointment, participants will provide signed informed consent, finish self-report measures, and be evaluated in person to determine the presence of at least one weekly binge eating episode using the overeating section of the Eating Disorder Examination. Participants will also have their height, weight, blood pressure, and waist circumference measured at this time. Baseline appointment will take place in a private room at the UNC Department of Family Medicine. If all inclusion criteria are met, participants will be randomly assigned to one of the two treatment conditions. There will be a brief waiting period between the initial consent discussion and obtaining consent for this study. In addition, consent will be obtained by research assistants affiliated with this study, other than the study PI.

7. Study Intervention

[An interventional study may involve a drug, device, biologic agent, or a medical, surgical, dental, radiological, nutritional, neurological, or behavioral intervention. The study may use an experimental design (e.g. a randomized trial) or it may use an observational design (e.g., a single-arm study or study in which the physician and patient choose from among available treatment regimens). **Complete only the sections below that are relevant to your study; enter N/A otherwise.**]

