8.3. Enrollment / Baseline (Day 0)

If participants are eligible for the study, the applicant will be given a date and time to meet with the PI and will be provided an email link to access the self-report measures associated with this study. At appointment, participants will provide signed informed consent, finish self-report measures, and be evaluated in person to determine the presence of at least one weekly binge eating episode using the overeating section of the Eating Disorder Examination. Participants will also have their height, weight, blood pressure, and waist circumference measured at this time. Baseline appointment will take place in a private room at the UNC Department of Family Medicine. If all inclusion criteria are met, participants will be randomly assigned to one of the two treatment conditions.

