9.1. Outcome Measures for Evaluation of Feasibility / Tolerability

To assess the feasibility of recruiting adult, AA women to the proposed study, the percent of eligible women who were enrolled and retained in the study will be examined and reasons for nonparticipation and attrition will be documented. Feasibility will also be determined by calculation of point and interval estimates (95% confidence intervals using sample size methods) of the feasibility parameters (proportion/percentages in terms of eligibility, participation, retention; means/medians for attendance at intervention sessions) and bivariate frequency distributions.

Question of Interest	Feasibility Measures
Can we recruit our target population?	# of screened and eligible participants, and proportion of eligible screens who enroll
Will participants do what they are asked to do?	Adherence to study protocol (e.g. session attendance, homework completion)
Are the assessments too burdensome?	Proportion of planned assessments completed; duration of assessment visits
Will participants stay in the study?	% of study retention and reasons for dropouts
Is AAT + NUTR acceptable to study participants?	Semi-structured telephone interviews (n=15-20) will be conducted to receive feedback on intervention and suggestions for improvement.

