11.2. Assessment of Safety

To minimize emotional distress, if participants cite this concern, they will be provided the option to a) pause

and regroup; and/or b) finish the survey at a later time. If the previous is not sufficient, and participants report experiencing significant distress, participants will be provided the number to Hopeline (<https://www.hopeline-nc.org>; [contact]), a North Carolina crisis line and to the local emergency room.

Participants who experience significant distress will also be asked permission to provide their contact information to the PI ([name]). [name], who is a licensed clinical social worker, will contact those

participants on the next day. [name] will also be updated immediately on all participants who experience

significant distress.

Depression – Beck Depression Inventory

Using the total score (from all added scores on the BDI), the following interpretation applies:

Total Score	Range of Depression
0 – 13	Minimal
14 – 19	Mild
20 – 28	Moderate
29 – 63	Severe

Potential participants who on initial assessment (or is there a screening assessment) have a BDI-II score of 29 or greater (“severe” depression) are excluded from the study (please see below).

If a participant’s total score is 20 or greater, this will be reported to the Principal Investigator (PI) or Project Director (PD) who will discuss their results, inquire about current status and

treatment, will **provide information on community resources for the treatment of depression, and document the conversation and actions taken.**

For question #9 “Suicidal Thoughts or Wishes”: If a participant chooses response option 1, 2 or 3, this will be reported to the PI or PD who will discuss the results, inquire about current status and treatment and document the conversation and actions taken (providing a detailed note of the discussion that will be maintained using the participant’s ID number). The participant will also be referred to their PCP, given a list of mental health providers in the community, and urged to seek treatment if they are not already receiving treatment.

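### Section 6.2 omits six exclusions that the Synopsis and Section 11.2 impose, and the protocol does not say which list governs

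*Combined protocol and SAP*

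**What the plan says.** Exclusions are stated in three places.

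- **Synopsis, key exclusion criteria.** Eight exclusions, including "involved in a weight loss program, have a history of anorexia nervosa, engage in purging" and "concurrent intravenous drug users or consume >4 alcoholic beverages/day".
- **Section 6.2.** Ten exclusions under the sentence "Any individual who meets one or more of the following criteria will be excluded from participation". Unlike the Synopsis list, this one is not labelled as a selection.
- **Section 11.2.** One further exclusion, inside the safety text: "Potential participants who on initial assessment (or is there a screening assessment) have a BDI-II score of 29 or greater". The words in brackets are an unresolved drafting question.

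Sections 6.4 and 8.3 describe entry in the same terms. Each begins "If participants are eligible for the study, the applicant will be given a date and time to meet with the PI", and after the baseline appointment each says "If all inclusion criteria are met, participants will be randomly assigned to one of the two treatment conditions". The exclusion criteria are not mentioned at that step.

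The primary feasibility measures in Section 5.4 (Table 2) include the number "of screened and eligible participants, and proportion of eligible screens who enroll". Sections 9.1 and 10.3 plan estimates with 95% confidence intervals for "proportion/percentages in terms of eligibility, participation, retention".

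**The concern.** A synopsis may be shorter than the full list. Here the full list lacks criteria that the synopsis imposes, and the safety section imposes one that neither of the other two contains. Staff who screen from Section 6.2 would apply a different rule from staff who screen from the Synopsis.

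Three things depend on which list is used:

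1. **Who is randomised.** A woman who purges, has a history of anorexia nervosa, or scores 29 or more on the depression inventory passes 6.2 but is excluded elsewhere. The follow-up steps in 11.2 for raised depression scores and suicidal thoughts apply under any list, so the issue is entry to the trial.
2. **Primary results.** In a feasibility trial, the number eligible and the eligibility percentage are themselves outcomes.
3. **Withdrawals.** Section 7.7 allows a participant to be withdrawn if she develops an exclusion criterion. Whether joining a weight-loss programme during the study qualifies depends on the list, and retention is also a primary measure.

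**Working it through.** The check is a comparison of the lists. The protocol states no count of exclusions to reproduce. Intravenous drug use and alcohol share a clause in the Synopsis and are counted as two criteria.

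| Exclusion | Synopsis | 6.2 | 11.2 |
|---|---|---|---|
| Pregnancy | yes | yes | – |
| Substance use treatment | yes | yes | – |
| Current treatment for disordered eating | yes | yes | – |
| Weight-loss programme | yes | – | – |
| Past anorexia nervosa | yes | – | – |
| Purging | yes | – | – |
| Intravenous drug use | yes | – | – |
| More than four alcoholic drinks a day | yes | – | – |
| BDI-II of 29 or more | – | – | yes |
| Minors | – | yes | – |
| Neonates | – | yes | – |
| Wards of the State | – | yes | – |
| Prisoners or detained persons | – | yes | – |
| Impaired decision-making | – | yes | – |
| Not English-speaking | – | yes | – |
| Likely abusive relationship | – | yes | – |
| **Total** | **8** | **10** | **1** |

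**Counts**

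- Shared by the Synopsis and 6.2: 3.
- Distinct exclusions: 8 + 10 − 3 + 1 = 16.
- Stated elsewhere but missing from 6.2: (8 − 3) + 1 = 6.
- In 6.2 only: 10 − 3 = 7. Three of these concern children or neonates, whom the over-18 criterion already rules out (taking 18 as the age of majority).
- Able to apply to an adult: 16 − 3 = 13, made up of 3 shared, 6 missing from 6.2, and 4 in 6.2 only.

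**Effect on the eligibility percentage.** The protocol gives no distribution of depression scores among women screened and no prevalence for the other criteria, so the number of women affected cannot be computed. Assume the percentage is eligible/screened. The number to be screened is 200 in the Synopsis and 160 in Section 6.1. One woman changing status then moves the percentage by 100/200 = 0.5 points or 100/160 = 0.625 points.

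**Effect on the enrolment proportion.** No direction can be given, because a tighter list can remove women from both numerator and denominator. As an illustration with equal uptake, 60/100 = 48/80 = 60%, so the proportion does not move.

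**Timing.** Sections 6.4 and 8.3 call a woman eligible before she finishes the self-report measures. Section 11.2 leaves open whether its exclusion is applied at screening or at the initial assessment. A woman excluded on the inventory could therefore be counted either as ineligible or as eligible but not enrolled.

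**Instrument.** Section 11.2 states the cut-off on the BDI-II. Sections 5.3 and 8.1 schedule the Beck Depression Inventory and cite reference 37, dated 1961.

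**The case against.** The strongest reply is that the three lists are compatible. Section 6.2 does not claim to be exhaustive and does not say that a woman who purges is admitted. Read together, the sections bar anyone whom any of them bars. That reading is possible, but no available section states it or links the three lists. Section 6.2 has the form of a complete list, and a screener who uses it as one makes no visible error.

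Several narrower objections stand in whole or in part:

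- The seven exclusions absent from the Synopsis would be no fault on their own, because that list is labelled as key criteria. The conflict lies in the six missing from 6.2, or five if drug use and alcohol are counted as one.
- The randomisation sentence in 6.4 and 8.3, read literally, would also bypass 6.2's own exclusions. It does not show that one list overrides another, only that the entry step contains no check on exclusions.
- Sections 5 and 6.3 place randomisation after all baseline assessments, and the depression inventory is one of them. The score should therefore exist before randomisation. What stays open is whether it is used to exclude and how the woman is then counted.
- The point at which a woman counts as eligible would need defining even with one list, because weekly binge eating is also confirmed at the appointment.
- The shift per woman is simply 1/N. If all 60 to be enrolled were exactly the eligible women (an assumption), the normal-approximation half-width is 1.96 × √(0.30 × 0.70/200) = 6.4 points, or 1.96 × √(0.375 × 0.625/160) = 7.5 points. About 12 to 13 women would have to change status to move the estimate by one half-width. A large numerical effect is therefore not shown.

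**Conclusion.** The eligibility rules are wrong as written. Six exclusions stated in the Synopsis or Section 11.2 are missing from the section that defines eligibility, and one of the six is an unfinished sentence. This is a contradiction between stated rules, and it affects who may be randomised and how primary feasibility measures are counted.

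The conclusion rests on the wording alone and is firm, with two limits. First, the absence of a governing rule can be confirmed only for the text available. Second, Section 8.2 mentions a web-based eligibility survey whose content is not shown, so the criteria applied in practice cannot be seen. No number of affected women and no change in the enrolment proportion is claimed. The point should be corrected, and it does not put the trial design itself in doubt.

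**What to change.** 1. Reconcile the Synopsis, Section 6.2 and Section 11.2 into one eligibility list, and use it identically in those places and on the screening form. Which criteria belong on it is for the sponsor to decide.
2. Resolve the timing query in 11.2 and confirm which version of the depression inventory is scheduled, if that exclusion is retained.
3. Reword the randomisation sentence in 6.4 and 8.3 so that every retained exclusion is checked first.
4. State in the analysis plan the step at which a woman counts as eligible for the Table 2 measures.
5. As a minor correction, align the clinic-list example in 6.1 (Black and White women, BMI above 30) with 6.2 and 6.3 (Black women, BMI of 25 or more).

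The cost is amendment wording and a revised screening form, with a short question for each retained criterion not already asked. No listed baseline measure is described as covering weight-loss programme involvement, intravenous drug use or alcohol intake, so those may need one unless the web survey already covers them.

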6.3. Strategies for Recruitment and Retention

Recruitment Strategy:

Using an IRB-approved waiver, a list of eligible participants (e.g., Non-Hispanic, AA women, BMI ≥ 25 kg/m²) at UNC Family Medicine will be generated from examining the electronic health record. We will then send an introductory letter via postal mail to all eligible participants. This letter will describe the study, and then provide information on opting out. Study staff will contact those who do not opt out and conduct an eligibility screen. If an individual is eligible, they will be given a date and time to meet with a research team member. Participants will be evaluated in person to determine the presence of at least one weekly binge eating episode using the overeating section of the Eating Disorder Examination. Participants will also complete height/weight measurements, provide signed informed consent, and finish self-report measures (See Table 1). Once all baseline assessments are complete, participants will be randomized to the AAT + NUTR intervention or wait-list control.

Retention Strategy:

Participants will receive \$25 for completing the assessment at 0, 4, and 6 months, for a total of \$75.00. Participants will be provided the incentive after participating in each assessment. If a participant withdraws prior to the completion of a particular assessment, the participant will only have access to incentives based on what assessments were previously completed. Because we wanted to prevent

coercion, we have purposely kept study incentives at a reasonable cost, and only at a level to offset the burden of participating in the study.

6.4. Consent Process

If participants are eligible for the study, the applicant will be given a date and time to meet with the PI and will be provided an email link to access the self-report measures associated with this study. At appointment, participants will provide signed informed consent, finish self-report measures, and be evaluated in person to determine the presence of at least one weekly binge eating episode using the overeating section of the Eating Disorder Examination. Participants will also have their height, weight, blood pressure, and waist circumference measured at this time. Baseline appointment will take place in a private room at the UNC Department of Family Medicine. If all inclusion criteria are met, participants will be randomly assigned to one of the two treatment conditions. There will be a brief waiting period between the initial consent discussion and obtaining consent for this study. In addition, consent will be obtained by research assistants affiliated with this study, other than the study PI.

7. Study Intervention

[An interventional study may involve a drug, device, biologic agent, or a medical, surgical, dental, radiological, nutritional, neurological, or behavioral intervention. The study may use an experimental design (e.g. a randomized trial) or it may use an observational design (e.g., a single-arm study or study in which the physician and patient choose from among available treatment regimens). **Complete only the sections below that are relevant to your study; enter N/A otherwise.**]

7.1. Intervention – Test Article (if applicable)

Description:

The Appetite Awareness Treatment (AAT) intervention includes eight 60-minute group sessions. All sessions involve didactic training, review of self-monitoring of eating episodes, interactive activities, and homework assignments to enable participants to practice learned skills. Participants will be provided a workbook, which will include session content, and self-monitoring forms.

The Behavioral Weight Loss (BWL) intervention is based on the curriculum for the Diabetes Prevention Program, and offers training in healthy eating, increasing physical activity, and achieving caloric balance.

Acquisition: [State how test article will be acquired, e.g., from manufacturer, IND/IDE Sponsor, UNC Investigational Drug Services, or internal, e.g., device developed by a UNC faculty or laboratory.]

N/A

Protocol <1005>

Formulation/Packaging/Labeling:

N/A

Storage and Stability:

N/A

Preparation and Administration:

N/A

Modification:

N/A

Accountability: [

N/A

7.2. Assignment Procedures

[If applicable to the study design, specify complete details of the plan for assigning enrolled participants to the treatment regimens.]

Matching and Stratification: (if applicable) [If applicable, specify exactly how matching and/or stratification of subjects will be accomplished]

N/A

Randomization, Concealment, and Blinding:

Randomization will be performed by Microsoft Excel and the PI will be blinded to all randomization. A research assistant will be responsible for supervising randomization.

Masking (Blinding):

Randomization will be performed by Microsoft Excel and the PI will be blinded to all randomization.

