8.2. Pre-Screening / Screening (Day -X to Day Y)

During recruitment, participants will not be directly contacted identified from privately held sources without the participant's permission. Methods that are the "least intrusive" will be used, and participants will be encouraged to contact the research team if they are interested in receiving more information about the study. Participants will self-refer to the study, and provided the link to participate in the survey. Participants will be contacted by email or telephone to after determining preliminary eligibility via a Qualtrics web survey. Recruitment will be managed by study investigators and research assistants. Potential participants will respond to notices by calling number on flyer or filling out the screening link, and will be screened to determine eligibility. If an individual is eligible, she will be given a date and time to meet with a research team member.

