10.6. Sample Size Rationale

Because this is a feasibility study, we are not prioritizing powering the sample to determine the efficacy of the AAT intervention. However, we ran conservative tests for statistical power incorporating parameters from our preliminary study using G*Power. Based on our analysis, we determined that a sample of 60, evenly allocated between treated and control groups, is sufficiently powered (.80) to identify large standardized mean differences in binge eating ($d = .74$) (Aim #2). The sample, however, is underpowered to determine differences in weight. Because this study is exploratory, we are prioritizing feasibility, and an exploration of differences, rather than determining efficacy. This is a pilot study, If this pilot study is successful, we will conduct a larger study with a greater sample of participants and test the AAT intervention for a longer duration.

11. Safety Monitoring and Management

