12.9.1. Data Collection and Management Responsibilities

Study data will be collected and managed using REDCap electronic data capture tools hosted at the University of North Carolina at Chapel Hill. REDCap (Research Electronic Data Capture) is a secure, web-based application designed to support data capture for research studies, providing: 1) an intuitive interface for validated data entry; 2) audit trails for tracking data manipulation and export procedures; 3) automated export procedures for seamless data downloads to common statistical packages; and 4) procedures for importing data from external sources.

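### Section 7.2 randomizes in Excel under a research assistant, describes no concealment mechanism, and does not separate that assistant from the staff who recruit and consent

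*Combined protocol and SAP*

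**What the plan says.** Section 7.2 (Assignment Procedures) has a heading that covers randomization, concealment and blinding. The text beneath it is two sentences: "Randomization will be performed by Microsoft Excel and the PI will be blinded to all randomization", and "A research assistant will be responsible for supervising randomization". Section 5 (Study Design) repeats both. The template prompt asks the authors to "specify exactly how matching and/or stratification of subjects will be accomplished", and the answer is N/A. No sequence type, blocking, list holder or release step appears in 7.2 or in section 5.

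On who enrols, section 6.4 says "consent will be obtained by research assistants affiliated with this study, other than the study PI", and section 8.2 says "Recruitment will be managed by study investigators and research assistants".

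On timing, section 6.3 says "Once all baseline assessments are complete, participants will be randomized to the AAT + NUTR intervention or wait-list control". Sections 6.4 and 8.3 place consent, the measurements and the interview that confirms weekly binge eating at the baseline appointment, with assignment following if the criteria are met.

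On arm sizes, section 10.6 bases its power statement on "a sample of 60, evenly allocated between treated and control groups". The synopsis and sections 3.1 and 5.1 give 24 per arm instead.

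On the data system, section 12.9.1 says "Study data will be collected and managed using REDCap electronic data capture tools".

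**The concern.** Concealment means that nobody deciding whether a woman enters the trial can know or guess her arm beforehand. The plan gives randomization to a member of a staff group that also recruits and consents, and it describes nothing that keeps the next assignment from those doing the enrolling. The one stated safeguard, blinding of the PI, protects against the PI's own influence. It does not act on the research assistants who obtain consent.

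Two features make this more than a formality. First, eligibility rests on a semi-structured interview about binge frequency, which leaves room for judgement just before assignment. Second, the arms are four months of group sessions or a wait-list. Assignments are therefore evident once made, and staff may prefer one arm for a particular woman. If the next arm could be foreseen, the eligibility judgement or the effort to persuade could shift with it. The arms would then differ at entry in ways such as motivation, and adjusting for baseline scores, as section 10.3 plans for Aim 2, does not remove differences in what was not measured.

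A lesser matter is that 7.2 contains nothing to produce the equal arms on which the power statement rests.

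**Working it through.** **1. Roles set side by side**

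| Step | Who | Where |
|---|---|---|
| Recruitment | Investigators and research assistants | 8.2 |
| Consent | Research assistants, not the PI | 6.4 |
| Baseline appointment | A research team member (5, 6.3) or a meeting with the PI (6.4, 8.3) | as shown |
| Randomization | Excel, supervised by a research assistant | 5, 7.2 |
| Blinded to randomization | PI | 5, 7.2 |

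The staff category that consents is the category that randomizes. No section says that the supervising assistant is one of those who enrol, and no section says that this person is separate. The blinded person is not the one who obtains consent.

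**2. Does randomizing after baseline close the gap?** It fixes the order of events. It protects only if the next assignment is unknown while eligibility and consent are being settled. If that assignment can be foreseen, the knowledge comes before the decision whatever the formal order. The ordering is necessary but not sufficient.

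**3. Reproducing the power figure**

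Inputs: d = 0.74, N = 60, equal arms, power 0.80 (10.6). The significance level and sidedness are not stated there. I assume two-sided 0.05, in line with the 95% intervals in 10.3.

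Formula: two-sample t-test with df = n1 + n2 − 2 and noncentrality d × √(n1·n2/(n1 + n2)).

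At 30/30: 0.74 × √(900/60) = 0.74 × 3.873 = 2.866, with df = 58. Power = 0.805, so the stated 0.80 is reproduced. One-sided 0.05 gives 0.882 and does not reproduce it.

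**4. What an unprotected split would cost**

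Assumption: Excel is used for unrestricted simple randomization, so the size of one arm is Binomial(60, 0.5). This is one reading of 7.2; the text does not say.

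- P(exactly 30/30) = C(60,30)/2^60 = 0.103.
- P(36/24 or worse, either direction) = 2 × P(X ≤ 24) = 0.155.

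| Split | Noncentrality | Power | P(this split or worse) |
|---|---|---|---|
| 30/30 | 2.866 | 0.805 | 1 |
| 24/36 | 0.74 × √(864/60) = 2.808 | 0.789 | 0.155 |
| 22/38 | 0.74 × √(836/60) = 2.762 | 0.775 | 0.052 |
| 20/40 | 0.74 × √(800/60) = 2.702 | 0.757 | 0.014 |

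Weighting the power at each split by its binomial probability gives an expected power of 0.798. The average loss is 0.805 − 0.798 = 0.007, or 0.7 percentage points. At 22/38, the edge of the 95% range of splits, the loss is 0.805 − 0.775 = 0.030.

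For scale, the other sample size in the document, 24 per arm, gives 0.709. The pilot's 88% retention (section 2.2) applied to 30 per arm leaves 30 × 0.88 = 26.4; at 26 per arm, power is 0.744. Both matter far more than chance imbalance.

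**The case against.** The strongest reply is that the documents are silent rather than wrong. Section 7.2 speaks of one research assistant and 6.4 of several, so the roles may well be held by different people. The N/A answers the prompt on matching and stratification, not a question about blocking. Excel can produce a restricted list, and the fixed arm sizes of 24 may mean that one is intended. The PI is not remote from enrolment: applicants are scheduled to meet the PI (6.4, 8.3) and investigators share in recruitment (8.2), so blinding the PI is a real, if partial, safeguard. Consent and baseline already precede assignment. Finally, the primary aim is feasibility, and 10.6 calls the efficacy comparison exploratory.

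Much of this stands, and it limits what can be said. A reader might infer that allocation is in fact unconcealed, that the spreadsheet lies open to recruiters or can be re-drawn, or that research assistants carry out the baseline assessments. No section says any of these. A reader might also infer that unblocked assignment would leave treatment groups too small to run, but the plan gives only a group format, with no cohort size and no minimum group size.

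The reply does not supply a mechanism. Nothing in the plan prevents the supervising assistant from also enrolling, and the PI's blinding does not reach those who obtain consent. Nor is it easy to sustain, because the PI supervises the clinicians weekly (7.3) and supervises the sessions (12.8). The exploratory status lowers the stakes. It does not remove them, since 10.6 looks to a larger study if this one succeeds.

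**Conclusion.** The concern holds in this form: the stated method includes no described concealment mechanism, and it does not assure separation between the assistant who randomizes and the staff who recruit and consent. With interview-based eligibility and unmasked arms, a foreseeable assignment could bias enrolment and, through it, the Aim 2 comparison. The documents give no basis for putting a number on that bias. Whether it would occur depends on who holds the list and who can see it, which the plan does not say.

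The even-split point is true but minor. It might be read as undermining the power statement, and it does not: 0.80 reproduces at 0.805, and simple randomization would bring expected power to about 0.798. Those figures assume a two-sided 5% t-test on all 60 women and unrestricted randomization.

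The change is worth making before the first woman is randomized, because the analysis cannot repair selection at entry.

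**What to change.** Replace the text of 7.2, and its copy in section 5, with a procedure along these lines.

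- An existing team member with no recruitment, consent or assessment role generates a 1:1 list in randomly permuted blocks, long enough for the enrolment target.
- Block sizes vary and are not disclosed to enrolling staff. Because the arms are evident once assigned, a fixed block size would let staff work out the later assignments in each block.
- Each assignment is released one at a time, only after eligibility, consent and baseline data have been entered. The release is through the REDCap system already in use, or by sequentially numbered, opaque, sealed envelopes if that is not practicable.
- Staff who recruit, consent or assess have no access to the list.

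The blocks also keep the arms close to equal, which settles the minor point about 10.6.

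The cost is a few hours of set-up and no new staff. The downside is that one member of the team must stay out of enrolment and assessment.
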